2.4 Endpoints

The primary endpoint on this study is defined as completion of all study drug over the first 4 weeks of study treatment (initial and crossover treatment phases).

Secondary endpoints include number of bowel movements per week, as captured on the Patient bowel movement diary (**Appendix F**), stool quality as measured by the Bristol Stool Scale (**Appendix G**), safety defined as the rate of drug-related adverse events experienced assessed according to the NCI's CTCAE v4.03 toxicity criteria, and health related quality of life and pain measures as assessed by the PAC-SYM, PAC-QOL, and BPI-sf, within the first 4 weeks of study treatment (see **section 9.3.3**).

Exploratory endpoints will include drug administration compliance as measured by weekly pill counts by a member of the study team, healthcare resource utilization as defined by the number of number of emergency room visits, hospitalizations, telephone encounters, and EPIC mychart

encounters related to signs and symptoms of constipation, and patient preference (yes/no) for naloxegol to treat OIC as defined by choice of participation in the optional extension phase of the study.

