6.0 Measurement of Effect

6.1 Safety/Tolerability

Analyses will be performed for all patients having received at least one dose of study drug. The study will use the NCI CTCAE v4.03 (<http://ctep.cancer.gov/reporting/ctc.html>) for reporting of adverse events. Safety will be assessed within the first 4 weeks of study treatment.

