6.2 Feasibility Assessment

The primary endpoint on this study is defined as completion of all required study drugs over the first 4 weeks of study treatment (initial and cross-over treatment phases).

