7.1 Adverse Event Monitoring

Adverse event data collection and reporting, which are required as part of every clinical trial, are done to ensure the safety of subjects enrolled in the studies as well as those who will enroll in future studies using similar agents. AEs are reported in a routine manner at scheduled times during a trial. Additionally, certain AEs must be reported in an expedited manner to allow for optimal monitoring of patient safety and care.

As far as possible, each adverse event should be evaluated to determine:

- duration (start and end dates)
- severity (grade)
- seriousness
- relationship to study agent
- action taken (i.e., none, study agent modification, medical intervention)
- outcome (i.e., resolved without sequelae, resolved with sequelae, ongoing)

AE monitoring begins at the time of informed consent signature and ends 28 days following the last administration of study treatment.

All patients experiencing an AE, regardless of its relationship to study drug will be monitored until:

- the event resolves or the symptoms or signs that constitute the event return to baseline;
- any clinically significant abnormal laboratory values have returned to baseline;
- there is a satisfactory explanation other than the study drug for the changes observed; or
- death.

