Preparation: Given its oral formulation, there is no product preparation required. IDS will prepare 14-day and 28-day supplies of naloxegol for dispensing to subjects according to randomization assignment and phase of study participation.

Route of administration for this study: Naloxegol will be administered as a single 25-mg tablet, once daily. Subjects will be instructed to take naloxegol on an empty stomach 1 hour before breakfast or 2 hours after their first meal of the day.

Side effects: The most common side effects associated with naloxegol are gastrointestinal in nature: abdominal pain, diarrhea, nausea, flatulence, vomiting, headache, and excessive sweating. Patients taking naloxegol may also experience additional symptoms of opioid withdrawal, including chills, anxiety, irritability, and yawning. There is also risk of developing abdominal or intestinal wall perforation.

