9.3.2 Safety Endpoint

Safety endpoints will be evaluated by monitoring AEs from clinical and laboratory reporting. Adverse events will be classified according to the NCI-CTCAE version 4.03. Trends in the distribution and severity of the AEs across the study groups will be assessed by examining the count of total AEs and count of AEs at each severity level over the course of the 2 weeks for the initial treatment and over the 2 weeks of the crossover treatment phases of the study.

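### The planned safety analysis covers only the two 2-week treatment phases, so adverse events collected in the washout, the optional extension and the 28-day follow-up enter no planned table.

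*Combined protocol and SAP*

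**What the plan says.** Section 6.1 defines the safety population broadly: "Analyses will be performed for all patients having received at least one dose of study drug". It then limits the period: "Safety will be assessed within the first 4 weeks of study treatment". Section 2.4 puts the same 4-week limit on the secondary endpoints, among them safety, defined there as the rate of drug-related AEs. Section 6.2 shows what the 4 weeks mean, because it sets the primary endpoint "over the first 4 weeks of study treatment (initial and cross-over treatment phases".

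Section 9.3.2 examines total AE counts and counts by severity "over the course of the 2 weeks for the initial treatment and over the 2 weeks of the crossover treatment phases of the study". The synopsis says the same.

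Collection is wider. Section 7.1 states: "AE monitoring begins at the time of informed consent signature and ends 28 days following the last administration of study treatment". Sections 4.1 and 5.4.1 require daily AE collection in the extension. Sections 4.8, 5.5 and 5.6 continue it through the end-of-study visit and 28 days of follow-up. As far as the broken table can be read, the Schedule of Events also marks AE collection on Days 15-17.

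**The concern.** Secondary objective 3 (section 2.2) has two limbs: to describe the AEs seen with daily naloxegol in these patients, and to compare them with those seen under usual care. The two 14-day windows suit the comparison. They serve the description poorly, because each patient contributes at most 14 naloxegol days while up to 84 further days are observed and recorded.

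Followed as written, the plan would report a naloxegol safety result without the longer-exposure data the trial has already collected. Events in the 3 days after Arm A stops naloxegol would belong to neither window, and no rule assigns them to a treatment. Section 1.4 says that the earlier naloxegol trial in cancer patients closed early for poor accrual, so longer exposure in this setting is worth reporting.

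**Working it through.** The plan gives no figure on this point. Its only sample-size figure, 80% power in section 9.2, was checked for completeness. With 50 patients and rates of 70% and 85%, the exact one-sided test rejects at 41 or more completers, with type I error 0.040 and power 0.791. That agrees with the stated 80%, and nothing below changes it.

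**Step 1. Collection against analysis, in nominal days.**

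| Phase | Length (days) | AEs collected | In a planned safety analysis |
|---|---|---|---|
| Initial treatment, Days 1-14 | 14 | yes | yes |
| Washout, Days 15-17 | 3 | yes | no |
| Crossover, Days 18-31 | 14 | yes | yes |
| Extension, from Day 32 | 84 | yes, daily | no |
| Follow-up after last treatment | 28 | yes | no |

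The exclusion of the extension and follow-up rests on sections 2.4 and 6.1. The exclusion of the washout rests on the windows in section 9.3.2.

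**Step 2. One patient.**
- Completes the extension: collected days from Day 1 = 14 + 3 + 14 + 84 + 28 = 143. Analysed days = 14 + 14 = 28, and 28/143 = 20%.
- Same patient, naloxegol days only: 14 + 84 = 98, of which 84 are outside, and 84/98 = 86%.
- Stops at Day 31: collected days = 14 + 3 + 14 + 28 = 59, and 28/59 = 47%. All 14 naloxegol days are inside.

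Section 4.1 gives the extension as 84 days, but Days 32-116 inclusive is 85. Using 85 gives 85/99 = 86%, so the conclusion is unchanged.

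**Step 3. The whole trial.** Extension uptake is not in the documents. Assume 50 treated patients who complete each phase they enter, with a proportion *u* continuing. Naloxegol days inside the windows = 50 × 14 = 700. Days outside = 50 × *u* × 84 = 4,200*u*. Share outside = 4,200*u* / (700 + 4,200*u*).

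| Uptake *u* | Days outside | Share outside |
|---|---|---|
| 10% | 420 | 420/1,120 = 38% |
| 25% | 1,050 | 1,050/1,750 = 60% |
| 50% | 2,100 | 2,100/2,800 = 75% |
| 100% | 4,200 | 4,200/4,900 = 86% |

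The share passes one half when 84*u* > 14, that is *u* > 1/6. In patients, 8 of 50 gives 8 × 84 = 672 days, below 700, and 9 of 50 gives 756, above it.

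**Step 4. Whether washout events can matter.** Section 4.1 bases the 3 days (72 hours) on a 10-hour half-life, while section 1.2 reports mean terminal half-lives of 14.1 to 20.3 hours. Five half-lives on those figures is 70.5 to 101.5 hours. The two sections need reconciling. For the analysis, it means an event on Days 15-17 in Arm A cannot be assumed unrelated to naloxegol.

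**The case against.** The best defence is that the window is deliberate and consistent. Sections 2.4, 6.1 and 9.3.2 and the synopsis agree. Only the two randomised phases allow a comparison with usual care. The extension is optional and uncontrolled, and its stated analysis role is patient preference. This stands for the comparison, which should stay as it is. It does not answer the descriptive limb of objective 3.

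It can also be said that the opening of section 9.3.2 has no time limit, and that the two windows attach only to trends across groups. That is a fair reading of 9.3.2 alone, but 2.4 and 6.1 impose the limit and no section offers another tabulation.

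Four stronger readings are tempting, and the documents do not support them:

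- *Extension events go unreviewed.* They do not. Under section 10.6 the DSMB receives a summary of all AEs every 6 months, and section 7.6 carries serious-event reporting to 28 days after the last dose. What is missing is a planned trial result.
- *The 4 weeks end on Day 28 and cut off the last crossover days.* Sections 2.4 and 6.2 define the 4 weeks as the two treatment phases, so Days 29-31 are included.
- *Most naloxegol exposure is left out.* That holds only above about 1 in 6 uptake.
- *The perforation warning in section 8.1 shows that the window hides this harm.* The warning says nothing about timing. Section 4.6 says cases with related drugs came soon after starting, and every treated patient's first naloxegol exposure falls inside a window. One qualification remains: an Arm A patient who continues has been off naloxegol on Days 15-31 and restarts on Day 32, outside the analysis.

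**Conclusion.** The point holds as a gap between what is collected and what is analysed. AEs from the washout, extension and follow-up enter no planned safety analysis, although describing the AEs of daily naloxegol is part of objective 3.

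The 86% figure applies to a patient who completes all 84 extension days. The trial-level share runs from 38% at 10% uptake to 86% at full uptake, assuming 50 treated patients who complete each phase they enter. Early stopping in the extension lowers these shares, and early stopping on naloxegol in the first two phases reduces the days inside the windows.

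The primary endpoint, the power and the randomised comparison are unaffected. This is a cheap improvement to the plan and does not threaten its main conclusion.

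**What to change.** 1. Keep the 4-week naloxegol versus usual care comparison, and state that it is the only between-treatment comparison of AEs.
2. Add an assignment rule: each AE, washout included, belongs to the most recent treatment until the next treatment starts or until 28 days after the last dose, whichever comes first. If washout events are also to enter the comparison, use rates per patient-week, because the first period would then span 14 + 3 = 17 days against 14.
3. Add one descriptive table by phase (initial, washout, crossover, extension, follow-up), split by most recent treatment. Show patients with any event, patients with a grade 3 or higher event, and events per patient-week with the exposure time. Include the follow-up of patients who decline the extension.
4. Amend sections 2.4, 6.1 and 9.3.2 so that the 4-week limit applies to the comparison only. Reconcile the 84-day and 85-day extension counts, and the 28-day follow-up with the 30-day monitoring period in section 7.6.4, so that the denominators are fixed.

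The cost is one table and a few sentences. No new data and no change in sample size are needed. The downside is that the extension rows have no comparator and come from patients who chose to continue naloxegol, so they can be read as description only.

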6.2 Feasibility Assessment

The primary endpoint on this study is defined as completion of all required study drugs over the first 4 weeks of study treatment (initial and cross-over treatment phases).

6.3 Efficacy Assessment

The efficacy of treatment with naloxegol versus treatment with usual care will be evaluated by the number of bowel movements per week, as captured on the Patient Bowel Movement Diary, and the stool quality as defined by the Bristol Stool Scale. These measures will be assessed within the first 4 weeks of study treatment.

6.4 Quality of Life

Quality of Life will be assessed by the following instruments: PAC-SYM, PAC-QOL, and BPI-sf. These instruments are described further in Sections 5.1.13.5-5.1.13.7. Quality of life will be assessed within the first 4 weeks of study treatment.

7.0 ADVERSE EVENTS

An adverse event (AE) is any untoward medical occurrence in a patient receiving study treatment, which does not necessarily have a causal relationship with this treatment. An AE can therefore be any unfavorable and unintended sign (including a clinically significant abnormal laboratory finding), symptom, or disease temporally associated with the use of an experimental intervention, whether or not related to the intervention.

Progression of the cancer under study or events which are unequivocally due to disease progression should not be reported as an AE during the study (unless it is considered to be drug related by the investigator).

7.1 Adverse Event Monitoring

Adverse event data collection and reporting, which are required as part of every clinical trial, are done to ensure the safety of subjects enrolled in the studies as well as those who will enroll in future studies using similar agents. AEs are reported in a routine manner at scheduled times during a trial. Additionally, certain AEs must be reported in an expedited manner to allow for optimal monitoring of patient safety and care.

As far as possible, each adverse event should be evaluated to determine:

- duration (start and end dates)
- severity (grade)
- seriousness
- relationship to study agent
- action taken (i.e., none, study agent modification, medical intervention)
- outcome (i.e., resolved without sequelae, resolved with sequelae, ongoing)

AE monitoring begins at the time of informed consent signature and ends 28 days following the last administration of study treatment.

All patients experiencing an AE, regardless of its relationship to study drug will be monitored until:

- the event resolves or the symptoms or signs that constitute the event return to baseline;
- any clinically significant abnormal laboratory values have returned to baseline;
- there is a satisfactory explanation other than the study drug for the changes observed; or
- death.

7.2 Severity

All AEs will be graded according to the NCI CTCAE v4.03. The NCI CTCAE v4.03 is available at <http://ctep.cancer.gov/reporting/ctc.html>

If no CTCAE grading is available, the severity of an AE is graded as follows:

Mild (grade 1): the event causes discomfort without disruption of normal daily activities.

Moderate (grade 2): the event causes discomfort that affects normal daily activities.

Severe (grade 3): the event makes the patient unable to perform normal daily activities or significantly affects his/her clinical status.

Life-threatening (grade 4): the patient was at risk of death at the time of the event.

Fatal (grade 5): the event caused death.

7.3 Seriousness

A “serious” adverse event (SAE) is defined in regulatory terminology as any untoward medical occurrence that:

1. Results in death.
If death results from (progression of) the disease, the disease should be reported as the event itself.
2. Is life-threatening.
The patient was at risk of death at the time of the event; it does not refer to an event that hypothetically might have caused death if it were more severe.
3. Requires in-patient hospitalization or prolongation of existing hospitalization.
Note: Hospitalization (including hospitalization for an elective procedure) for a pre-existing condition which has not worsened does not constitute a serious adverse event.
4. Results in persistent or significant disability or incapacity.
5. Is a congenital anomaly/birth defect
6. Is an important medical event
Any event that does not meet the above criteria, but that in the judgment of the investigator jeopardizes the patient, may be considered for reporting as a serious adverse event. The event may require medical or surgical intervention to prevent one of the outcomes listed in the definition of "Serious Adverse Event".
For example: allergic bronchospasm requiring intensive treatment in an emergency room or at home; convulsions that may not result in hospitalization; development of drug abuse or drug dependency.

Given that the Investigator's perspective may be informed by having actually observed the event, and the Sponsor is likely to have broader knowledge of the drug and its effects to inform its evaluation of the significance of the event, if either the Sponsor or the Investigator believes that the event is serious, the event will be considered serious.

7.4 Relationship

The relationship to the IP of each AE/SAE will be evaluated by the investigator using the following levels:

- **Not related:** The temporal relationship of the clinical event to the administration of IP makes a causal relationship unlikely; and other drugs, therapeutic intervention or underlying conditions provide a sufficient explanation for the observed event.
- **Related:** The temporal relationship of the clinical event to the administration of the IP makes a causal relationship possible; and other drugs, therapeutic interventions or underlying conditions do not provide sufficient explanation for the observed event. A clear-cut temporal association with improvement on cessation of the study drug or recurrence upon rechallenge may also be observed.

7.5 Prior experience

Expected events are those that have been previously identified as resulting from administration of the agent. An AE is considered unexpected, for expedited reporting purposes only, when either the type of event or the severity of the event is not listed in the current known adverse events listed in the agent clinical experience section of this protocol, the Investigator Brochure, or the current Product Label.

7.6 Reporting Requirements for Adverse Events

7.6.1 Safety Reporting

A. **Principal Investigator** must be notified within 24 hours of learning of any SAE, regardless of attribution, occurring during the study or within 28 days of the last administration of the study drug.

B. The **UCSD Human Research Protections Program (HRPP) and Moores Cancer Center Data and Safety Monitoring Board (DSMB)** must be notified within 10 business days of "any unanticipated problems involving risk to subjects or others" (UPR).

The following events meet the definition of UPR:

1. Any serious event (injuries, side effects, deaths or other problems), which in the opinion of the Principal Investigator was unanticipated, involved risk to subjects or others, and was possibly related to the research procedures.
2. Any serious accidental or unintentional change to the IRB-approved protocol that alters the level of risk.
3. Any deviation from the protocol taken without prior Institutional Review Board (IRB) review to eliminate apparent immediate hazard to a research subject.
4. Any new information (e.g., publication, safety monitoring report, updated sponsor safety report), interim result or other finding that indicates an unexpected change to the risk/benefit ratio for the research.
5. Any breach in confidentiality that may involve risk to the subject or others.
6. Any complaint of a subject that indicates an unanticipated risk or that cannot be resolved by the Principal Investigator.

C. This study sponsor is exempted from the IND Safety Reporting by the FDA.

AstraZeneca is responsible for NDA expedited safety reporting to FDA in accordance with local regulatory requirements. Investigators should provide all available information at the time of SAE Report Form completion. Investigators should not wait to collect additional information to fully document the event before notifying AstraZeneca of an SAE. When additional information becomes available, investigators should submit a follow-up SAE Report Form (separate from the initial report form) with the new information. Any follow-up information to an SAE also needs to be provided to AstraZeneca within 24 hours of learning of the new information.

AstraZeneca should be notified within one (1) calendar day of initial receipt from the site for all fatal and life-threatening cases and within five (5) calendar days of initial receipt from the site for all other SAEs.

When reporting to AstraZeneca, a cover page should accompany the MedWatch/AdEERs form indicating the following:

- Investigator Sponsored Study (ISS)
- The investigator's name and address
- The trial name/title and AstraZeneca ISS reference number (ESR-15-11108)

The Principal Investigator must also indicate, either in the SAE report or the cover page, the causality of events in relation to all study medications and if the SAE is related to disease progression, as determined by the principal investigator.

Send SAE report and accompanying cover page to AstraZeneca by email to AE Mailbox Clinical Trial (TCS) <[contact]> or by fax to [name] (US Fax number). Email is the preferred method.

7.6.2 Routine Reporting Requirements

- A. The **UCSD HRPP** must be notified of any AEs that are not unanticipated problems involving risk to subjects or others (non-UPRs) at the time of the annual Continuing Review.
- B. SAEs that do not require expedited reporting will be reported to AstraZeneca at least every month preferably using the MedDRA coding language for SAEs.

All SAEs must be reported to AstraZeneca, whether or not considered causally related to the investigational product. All SAEs will be documented. The Principal Investigator is responsible for informing the IRB and/or the Regulatory Authority of the SAE as per local requirements.

7.6.3 Pregnancy Reporting Requirements

If a patient becomes pregnant during the course of the study, naloxegol should be discontinued immediately. The **Principal Investigator** must be notified within 24 hours of any pregnancies occurring in a female patient or a female partner of a male patient. The Principal Investigator or designated site personnel will then inform AstraZeneca representatives no later than the end of the next business day of when he or she becomes aware of it.

Pregnancy itself is not regarded as an AE unless there is a suspicion that naloxegol may have interfered with the effectiveness of a contraceptive medication. Congenital abnormalities/birth defects, spontaneous miscarriages or ectopic pregnancy should be reported and handled as SAEs. Elective abortions without complications should not be considered AEs unless they were therapeutic abortions. The outcome of all pregnancies (spontaneous miscarriage, elective termination, ectopic pregnancy, normal birth, or congenital abnormality) should be followed up and documented. The outcomes of any conception occurring from the date of the first dose until 12 weeks after the date of last dose will be followed up and documented. The Investigator should follow-up with the study patient or the female partner of the study patient, even if the patient was discontinued from the study.

